8.2.2 Clinical Laboratory Testing

A list of clinical laboratory tests to be performed is provided in Appendix 2.

The clinical safety laboratory tests will be performed at a central laboratory. Samples for complete blood count (CBC) and chemistry should be obtained and analyzed based on central lab requirements. Laboratory safety tests may be performed at various unscheduled time points, if deemed necessary by the Investigator or designee.

8.2.3 Pregnancy Testing

Subject samples for pregnancy testing will be acquired pre-administration at the Screening and Week 6 visits in women of childbearing potential, as specified in the SoA (Section 1.3). All women of childbearing potential (defined in Appendix 4) must have a negative pregnancy test prior to administration of ¹²⁴I-AT-01 at the Day 1 and Week 6 visits to participate in the study. Samples for serum pregnancy tests must be drawn within 7 days prior to ¹²⁴I-AT-01 administration for all women of childbearing potential.

Prior to enrollment in the study, female subjects of childbearing potential and male subjects must be advised of the importance of avoiding pregnancy or partner pregnancy, respectively, during the trial, and the potential risks associated with an unintentional pregnancy. Contraceptive and barrier guidance and collection of pregnancy information is described in Appendix 4.

8.2.4 Unscheduled Safety Visits

Additional visits may be scheduled, as necessary, to ensure the safety and well-being of subjects. All additional exams should be fully documented in the source documents and on Unscheduled Visit CRFs, as appropriate.

8.3 Adverse Events, Serious Adverse Events, and Other Safety Reporting

The definitions of AEs and SAEs; the methods of recording, evaluating, and assessing causality of AEs and SAEs; and the procedures for completing and transmitting SAE reports are provided in Appendix 3.

Adverse events will be graded for seriousness, severity, and relationship to study drug treatment.

After obtaining informed consent, each subject must be given the names and telephone numbers of study site staff for reporting AEs and medical emergencies.

8.3.1 Time Period and Frequency for Collecting AE and SAE Information

All AEs and SAEs will be recorded from the time of informed consent until the final EOS telephone follow-up (~Week 10).

Throughout the study, every effort must be made to remain alert to possible AEs. If an AE occurs, the first concern should be for the safety of the subject. If necessary, appropriate medical intervention should be provided.

8.3.2 Method of Detecting AEs and SAEs

Adverse events may be spontaneously reported by the subject, obtained through non-leading questioning, or noted during examination of a subject.

When recording an AE, a diagnosis is always preferable; however, in the absence of a diagnosis, the Investigator should record each sign and symptom as an individual AE.

Medical or surgical procedures (e.g., cardiac ablation) should not be recorded as AEs. Rather, the condition for which the procedure was performed should be recorded.

Adverse events will be recorded from the time informed consent (Section 10.1.3) is obtained through the end of the study. The data will be recorded on the appropriate CRF, regardless of whether they are thought to be associated with the study or treatment with study drug.

Investigators are not obligated to actively seek SAE information from subjects that complete the study but are encouraged to notify the Sponsor or designee of any SAE occurring at any time after a subject has discontinued or completed the study that they judge may be reasonably related to treatment with study drug or study participation.

8.3.3 Follow-up of AEs and SAEs

All related SAEs must be followed until resolution, until the condition stabilizes, until the event is otherwise explained, or the subject is lost to follow-up. The Investigator is responsible for ensuring that follow-up includes any supplemental investigations as may be indicated to elucidate as completely as practical the nature and/or causality of the AE or SAE. This may include additional laboratory tests or investigations, histopathological examinations, relevant hospital records (i.e., discharge summary), or consultation with other health care professionals. The Investigator must ensure that all subject identifiers are redacted from supportive documentation prior to submission.

The Sponsor or designee may request that the Investigator perform or arrange for the conduct of supplemental measurements and/or evaluations. If a subject dies during participation in the study or during a recognized follow-up period, the Sponsor or designee should be provided with a copy of any postmortem findings, including histopathology.

New or updated information obtained during SAE follow-up should be recorded in the original/existing form(s); updates should be made to the relevant data in the EDC. If EDC is not available, then new or updated information should be recorded on a new paper SAE form; the original or prior paper SAE forms must not be re-used or altered. By signing the SAE form, the Investigator or designee attests to the accuracy and completeness of the data and that he/she has reviewed the report being submitted and approves it. If a paper form is used, the same information is to be captured in the EDC when EDC becomes available.

8.3.4 Regulatory Reporting Requirements for SAEs

Any SAE experienced by the subject between the time of the signing of the ICF and up to the EOS telephone call (approximately Week 10) must be recorded on an SAE form, regardless of the severity of the event or its relationship to treatment with study drug. Once the Investigator determines that the event meets the protocol definition of an SAE, the SAE must be reported to the Sponsor, or designee, within 24 hours.

Prompt notification of an SAE by the Investigator to the Sponsor is essential to meet the legal obligations and ethical responsibilities regarding the safety of subjects and the safety of a study intervention under clinical investigation.

Reporting of a SAE requires the following:

- Completion of the SAE Report Form details in the EDC, or if the EDC is not available, transmission of the paper SAE Report Form to the Sponsor or designee, via email as noted in the Study Manual. The SAE event is to be reported within 24 hours of the Investigator's knowledge of the event. If paper submission is used, the same information is to be entered into the EDC when EDC becomes available.
- Reporting of additional, follow-up information for previously reported SAEs should
 follow the same reporting timeframe and procedures as initial reports. New or updated
 information should be made to the relevant data in the EDC. If EDC is not available, new
 or updated information should be recorded on a new paper SAE form; the original or
 prior paper SAE forms must not be re-used or altered.
- Accompanying documentation, such as laboratory data, concomitant medication records, hospital records etc., should be redacted and transmitted to the Sponsor or designee as outlined in the Study Manual. In addition, the corresponding AE in the AE CRF (as applicable) should be updated to ensure all data points documented in the AE CRF are aligned with the matching data points on the SAE Report Form.

The Sponsor has a legal responsibility to notify health authorities about the safety of a study intervention under clinical investigation. The Sponsor will comply with country-specific regulatory requirements relating to safety reporting to the local regulatory authority, Institutional Review Boards (IRB)/Independent Ethics Committees (IEC), and Investigators.

An Investigator who receives an Investigator Safety Report describing an SAE or other specific safety information (e.g., summary or listing of SAEs) from the Sponsor will review and then file it along with the IB and will notify the IRB/IEC, as appropriate according to local requirements.

Investigator Safety Reports must be prepared for suspected unexpected serious adverse reactions (SUSAR) according to local regulatory requirements and Sponsor policy and forwarded to Investigators as necessary.

8.3.5 Pregnancy

The Investigator must report a pregnancy occurring in a female subject to the Sponsor or designee within 24 hours of the study site staff becoming aware of the pregnancy. In addition, if a female subject becomes pregnant within 12 weeks after last dose of study drug, the pregnancy must also be reported within 24 hours of the study site becoming aware of the pregnancy. The Investigator or study site staff must also follow the pregnancy until the outcome is known and submit the outcome as follow-up within 24 hours of notification of outcome. Follow-up Pregnancy Forms may be submitted as required as additional information is obtained. Although pregnancy occurring in a clinical study is not considered to be an AE or SAE, any pregnancy complication or elective termination of a pregnancy, for medical reasons, will be recorded as an AE or SAE and followed as such. Pregnancies in partners of male study subjects will similarly be monitored for the full duration of the pregnancy and/or followed through a definitive outcome (i.e., birth, or spontaneous or elective abortion). Pregnancy reporting must be submitted via email as noted in the Study Manual.

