2.3.2 Potential Risks

Clinically significant potential risks and their mitigation strategies are summarized in Table 1. As with all imaging studies involving radiopharmaceuticals, the greatest risks to subjects in this study are associated with reactions to the radiotracer and the radiation dose associated with the injected radionuclide and external x-rays associated with the CT component of the PET/CT scan. These risks are described in Sections 2.3.2.1 and 2.3.2.2.

Table 1: Protocol AT01-001: Risk Assessment

| Potential Risk | Rationale for Risk | Risk Mitigation Strategy |
|------------------------------|---|--|
| Study Intervention(s | | |
| Infusion-related reactions | As with all protein/peptide infusions, there is a potential for an infusion-related reaction (IRR) in subjects administered ¹²⁴ I-AT-01 (Doessegger 2015). | Subjects will be monitored during and following the administration of ¹²⁴ I-AT-01 and instructed to report any symptoms indicative of an IRR without delay (Section 7.1.1.1). |
| Immunogenicity | As with all therapeutic proteins, there is a potential for an immune response in subjects administered ¹²⁴ I-AT-01. | Subjects will be monitored during and following the administration of ¹²⁴ I-AT-01and instructed to report any symptoms indicative of an immune response without delay. |
| Radiation exposure | ¹²⁴ I-AT-01 contains radioactive iodine. | Subjects exposed to ¹²⁴ I-AT-01 will be pretreated with nonradioactive elemental iodine (¹²⁷ I), administered as potassium iodide (KI) at recommended doses prior to and for 3 days after dosing (Section 2.3.2.1). |
| | | Subjects must agree to prevent pregnancy during the study and for at least 90 days afterwards (Section 5.1). |
| Study Procedures | | |
| Exposure to SARS-CoV-2 virus | International guidelines (e.g., FDA Guidance on Conduct of Clinical Trials of Medical Products During the COVID-19 Public Health Emergency) on the conduct of clinical trials during the COVID-19 pandemic. | Section 2.3.2.2. |

Abbreviations: CT = computed tomography; ECG = electrocardiogram; FDA = United States Food and Drug Administration; PET = positron emission tomography; SpO₂ = peripheral blood oxygen saturation.

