5.1 Inclusion Criteria

Subjects are eligible to be included in the study only if all the following criteria apply:

- 1) Understands the study procedures and is capable of giving signed informed consent, as described in Appendix 1, which includes compliance with the requirements and restrictions listed in the informed consent form (ICF) and in this protocol.
- 2) Male or female \geq 18 years of age.
- 3) Has a history of AL or ATTR systemic amyloidosis with at least one organ with clinically demonstrable amyloid involvement defined by:
 - a) For AL systemic amyloidosis:
 - i) Positive tissue (e.g., fat-pad, gastrointestinal tract, etc.) biopsy for AL amyloid, and
 - ii) Achieved a hematologic very good partial response (VGPR) or complete response (CR) based on their most recent assessment and within 12 months of screening, and
 - iii) At least one of the following:
 - (1) Cardiac, renal, or liver biopsy positive for amyloid, or
 - (2) NT-proBNP \geq 650 pg/mL, or
 - (3) Left ventricle septal wall thickness ≥12 mm by echocardiogram or cardiac magnetic resonance (CMR), or
 - (4) 24-hour urine protein >500 mg, or
 - (5) Urine albumin-to-creatinine ratio (UACR) >300 mg/g.
 - b) For ATTR (wild type or variant) systemic amyloidosis:
 - i) Positive cardiac biopsy for ATTR amyloid, or
 - ii) At least two of the following:
 - (1) Positive extracardiac tissue (e.g., fat-pad, GI tract, etc.) biopsy for ATTR amyloid or positive transthyretin gene mutation associated with amyloid (obtained at any time), or
 - (2) Left ventricle septal wall thickness ≥12 mm by echocardiogram or CMR (in the absence of alternative causes), or
 - (3) Pyrophosphate (PYP) scintigraphy with myocardial uptake ≥grade 2 (or heart/contralateral chest ratio >1.5) using SPECT/CT scan if AL amyloidosis is excluded.

- 4) Able to undergo two PET/CT scans as part of the study, including ability to lie supine for up to 1 hour.
- 5) For women of childbearing potential: agreement to remain abstinent (refrain from heterosexual intercourse) or use contraceptive methods that result in a failure rate of <1% per year during the treatment period and for at least 90 days after the last dose of ¹²⁴I-AT-01.

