 - a) A woman is considered of childbearing potential if she is postmenarchal, has not reached a postmenopausal state (≥12 months of amenorrhea with no identified cause other than menopause), and has not undergone surgical sterilization (removal of ovaries and/or uterus). The definition of childbearing potential may be adapted for alignment with local guidelines or requirements.
 - b) Examples of contraceptive methods with a failure rate of <1% per year include bilateral tubal ligation, male sterilization, established, proper use of hormonal contraceptives that inhibit ovulation, hormone-releasing intrauterine devices, and copper intrauterine devices.
 - c) Contraception methods that do not result in a failure rate of <1% per year such as cap, diaphragm, or sponge with spermicide, or male or female condom with or without spermicide, are not acceptable.
 - d) The reliability of sexual abstinence should be evaluated in relation to the duration of the clinical trial and the preferred and usual lifestyle of the subject. Periodic abstinence (e.g., calendar, ovulation, symptothermal, or post-ovulation methods) and withdrawal are not acceptable methods of contraception.
- 6) For men: agreement to remain abstinent or use contraceptive measures and agreement to refrain from donating sperm, as defined below:
 - a) With female partners of childbearing potential, men must remain abstinent or use a condom plus an additional contraceptive method that together result in a failure rate of <1% per year during the treatment period and for at least 120 days (a spermatogenesis cycle) after the last dose of study intervention. Men must refrain from donating sperm during this same time period.

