10.4.2 Contraception Guidance

For Women of Childbearing Potential

Agreement to remain as abstinent (refrain from heterosexual intercourse) or use contraceptive methods that result in a failure rate of <1% per year during the treatment period and for at least 90 days after the last dose of study intervention.

- a. A woman is considered of childbearing potential if she is postmenarchal, has not reached a postmenopausal state (≥12 months of amenorrhea with no identified cause other than menopause), and has not undergone surgical sterilization (removal of ovaries and/or uterus). The definition of childbearing potential may be adapted for alignment with local guidelines or requirements.
- b. Examples of contraceptive methods with a failure rate of <1% per year include bilateral tubal ligation, male sterilization, established, proper use of hormonal contraceptives that inhibit ovulation, hormone-releasing intrauterine devices, and copper intrauterine devices.
- c. Contraception methods that do not result in a failure rate of <1% per year such as cap, diaphragm, or sponge with spermicide, or male or female condom with or without spermicide, are not acceptable.

The reliability of sexual abstinence should be evaluated in relation to the duration of the clinical trial and the preferred and usual lifestyle of the subject. Periodic abstinence (e.g., calendar, ovulation, symptothermal, or post-ovulation methods) and withdrawal are not acceptable methods of contraception.

For Men:

Agreement to remain abstinent or use contraceptive measures and agreement to refrain from donating sperm, as defined below:

a. With female partners of childbearing potential, men must remain abstinent or use a condom plus an additional contraceptive method that together result in a failure rate of <1% per year during the treatment period and for at least 30 days plus 90 days (a spermatogenesis cycle) after the last dose of study intervention. Men must refrain from donating sperm during this same time period

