10.4.3 Collection of Pregnancy Information

Female Subjects Who Become Pregnant

- The Investigator will collect pregnancy information on any female subject who becomes pregnant while participating in this study. The initial information will be recorded on the appropriate form and submitted to the Sponsor within 24 hours of learning of a subject's pregnancy.
- The subject will be followed to determine the outcome of the pregnancy. The Investigator will collect follow-up information on the subject and the neonate and the information will be forwarded to the Sponsor. Generally, follow-up will not be required for longer than 6 to 8 weeks beyond the estimated delivery date. Any termination of pregnancy will be reported, regardless of fetal status (presence or absence of anomalies) or indication for the procedure.
- While pregnancy itself is not considered to be an AE or SAE, any pregnancy complication or elective termination of a pregnancy for medical reasons will be reported as an AE or SAE.
- A spontaneous abortion (occurring at <22 weeks gestational age) or stillbirth (occurring at >22 weeks gestational age) is always considered to be an SAE and will be reported as such.
- Any post-study pregnancy related SAE considered reasonably related to the study intervention by the Investigator will be reported to the Sponsor, as described in Section 8.3.5.
 While the Investigator is not obligated to actively seek this information in former study subjects, he or she may learn of an SAE through spontaneous reporting.
- Any female subject who becomes pregnant while participating in the study will discontinue study intervention or be withdrawn from the study.

Male Subjects with Partners Who Become Pregnant

• The Investigator will attempt to collect pregnancy information on any male subject's female partner who becomes pregnant while the male subject is in this study. This applies only to male subjects who receive any study intervention.

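### Collection of partner pregnancies stops when the man leaves the study, well before his stated 120-day contraception period ends, and the women's rules also disagree, by 6 days

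*Protocol*

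**What the plan says.** **Contraception periods.**
- Women: Section 5.1, criterion 5, requires contraception or abstinence "during the treatment period and for at least 90 days after the last dose of ¹²⁴I-AT-01". Sections 2.3.2.1 and 10.4.2 also give 90 days from the last dose.
- Men with partners of childbearing potential: Section 5.1, criterion 6, has "for at least 120 days (a spermatogenesis cycle) after the last dose of study intervention". Sections 2.3.2.1 and 10.4.2 write the same total as 30 plus 90 days.
- Table 1 (Section 2.3.2) uses another starting point: "Subjects must agree to prevent pregnancy during the study and for at least 90 days afterwards". That counts from the end of the study, not from the last dose.

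**Pregnancy collection.**
- Women, Section 8.3.5: pregnancies in female subjects are reportable, and a further sentence extends this past dosing: "if a female subject becomes pregnant within 12 weeks after last dose of study drug, the pregnancy must also be reported within 24 hours".
- Women, Section 10.4.3: information is collected on "any female subject who becomes pregnant while participating in this study", with no mention of the 12-week extension.
- Partners, Section 10.4.3: the investigator attempts to collect information on any male subject's "female partner who becomes pregnant while the male subject is in this study", provided that he received study intervention.
- Partners, Section 8.3.5: pregnancies will be *similarly* monitored to outcome, with no window for when they must begin.

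**End of participation.** The final safety follow-up is 28 ± 3 days after the second administration (Section 4.1.4). Subjects withdrawn for reasons other than an infusion-related reaction have early termination (ET) activities within 7 days of the decision (Section 4.1.5).

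**The concern.** A contraception period states how long after dosing the sponsor wants conception avoided. If a pregnancy occurs in that period despite the advice, it is one the sponsor would want to know about. Here the collection rule for partners is tied to the man's presence in the study, not to his last dose. Under 10.4.3 a site can therefore stop collecting while the man is still under instruction to prevent conception.

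Early stopping is built into the design. A subject with no amyloid in the heart, liver, spleen or kidney on the Day 1 scan is discontinued after one dose (Sections 4.1.3.1, 7.1 and 8.1.4), as is one given heparin shortly before the second dose (Section 7.1.1.2). These men have been dosed, but an exit-based rule gives them the shortest collection period.

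At stake is the completeness of the pregnancy safety data. An uncomplicated partner pregnancy conceived in the gap would need neither a report nor outcome follow-up. In addition, two sections give sites different instructions on a 24-hour report.

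**Working it through.** This is date arithmetic, with days counted from the last dose received.

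**Inputs.** Men's contraception period 120 days (5.1; 30 + 90 = 120 in 2.3.2.1 and 10.4.2, so these agree). Women's period 90 days (5.1, 2.3.2.1, 10.4.2). Women's reporting window 12 weeks (8.3.5). Completer's exit at day 28 ± 3, that is 25 to 31 (4.1.4). ET within 7 days of the decision (4.1.5). Half-life 4.2 days (4.2.3).

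**Formula.** Uncovered days = contraception period − last day on which a new pregnancy must be collected.

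**Partners of male subjects.**
- Completers under 10.4.3: 120 − 31 = 89 to 120 − 25 = 95 days (120 − 28 = 92 at the nominal visit).
- If *similarly* in 8.3.5 imports the women's window: 12 × 7 = 84, and 120 − 84 = 36 days.
- Stopped after dose 1, early extreme (assumed: decision on the dosing day, ET on day 7): 120 − 7 = 113 days.
- Stopped after dose 1 near Week 6, for example for heparin within 7 days of the planned second dose (assumed: earliest exit at 42 − 7 = day 35): 120 − 35 = 85 days, and fewer for any later exit.

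Both early-stopping figures assume that ET ends participation; the protocol does not define when a withdrawn man is no longer in the study.

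**Women.**
- 8.3.5 against 5.1: 90 − 84 = 6 days. The 12 weeks run from the last dose, so withdrawal does not change this.
- Under Table 1, the period ends at 25 + 90 = 115 to 31 + 90 = 121 days after the second dose. Against 84 days the mismatch would be 31 to 37 days.

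**Radioactivity.** Section 4.2.3 treats ten half-lives as complete clearance: 10 × 4.2 = 42 days, about 6 weeks. Day 84 is 84 / 4.2 = 20 half-lives, which leaves 0.5^20, about one millionth of the activity, by physical decay alone.

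**The case against.** The best counter-argument is that the women's rules are cumulative. Section 8.3.5 adds the 12-week extension explicitly, and 10.4.3 nowhere says that reporting stops at study exit. A site must follow both, so 8.3.5 still binds. This stands. A reader might infer that women have 59 to 65 uncovered days (90 − 31 to 90 − 25) by treating 10.4.3 as overriding 8.3.5; the documents do not support that. A reader might also infer that early withdrawal widens the women's gap. It does not, because their window runs from the last dose.

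A second tempting reading is that radiation-exposed pregnancies go unreported. For women this fails on the protocol's own statement of clearance at about 6 weeks: the uncovered days 85 to 90 fall long after that. For men the protocol's stated basis is the spermatogenesis cycle, not residual activity.

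Third, 8.3.5 sets no cut-off for partners, and no stated window is not a short window. That is fair, and it is why the partner gap is attributed to 10.4.3. But 10.4.3 is then the only explicit limit that a site can apply.

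Fourth, there are partial backstops. Section 10.4.3 requires reporting of a post-study pregnancy-related serious adverse event (SAE) judged reasonably related, and always classes spontaneous abortion and stillbirth as SAEs. Section 8.3.2 encourages sites to notify related SAEs arising later. Neither covers an uncomplicated pregnancy, and sites need not actively seek these events.

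Finally, the 113-day figure is close to a worst case. Subjects stopped for infusion-related reactions go through both safety follow-ups instead of ET, and other withdrawals may come later.

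**Conclusion.** The point holds, and its weight lies in the partner rule in Section 10.4.3. For men who complete the study, 89 to 95 of the 120 days are uncovered under that section, or 36 if 8.3.5 is read as importing 12 weeks. For men stopped after one dose the gap ranges from about 113 days to about 85 or fewer, on the assumption that ET ends participation. The women's mismatch is minor: 6 days, plus the missing extension in 10.4.3 and the different starting point in Table 1.

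The conclusion concerns pregnancies conceived inside the protocol's own contraception periods; it does not claim that they would be radiation-exposed. With about 20 subjects, few such events are likely, and no endpoint, analysis or sample size is affected. It is a safety-reporting inconsistency worth correcting because the correction is inexpensive. No position is taken on which contraception period is right.

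**What to change.** Reconcile Sections 8.3.5, 10.4.3, 5.1, 10.4.2 and Table 1 so that the pregnancy-reporting window for female subjects and for partners of male subjects:
- is stated once and cross-referenced elsewhere;
- is counted from the last administration received;
- applies equally to completers and to subjects stopped early for any reason;
- does not end before whatever contraception period the reconciled protocol states for that sex.

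The sponsor should also settle whether the Table 1 period starts at the last dose or at the end of the study.

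The cost is protocol wording, telling subjects at exit to report a pregnancy within the window, and partner consent and outcome follow-up (already described in Section 10.4.3) for any additional pregnancy reported. No extra visit, dose or analysis is involved.
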